# Appendix A

12	
History of heart transplant or on a transplant list or with LV assistance device
	
Measured from all available data to and including the day of drug initiation in any diagnosis position and inpatient or outpatient care setting
 
Heart Transplantation            ICD-9 diagnosis: V42.1, V49.83, 996.83            ICD-10 diagnosis: Z94.1, Z76.82, T86.20, T86.21, T86.22            ICD-9 procedure: 33.6, 37.51            ICD-10 procedure: 02YA020, 02YA021, 02YA022            CPT-4 code: 33935, 33945
 
LVAD/Implantable Heart            ICD-9 diagnosis: V43.2x            ICD-10 diagnosis: Z95.811, Z95.812            ICD-9 procedure: 37.60, 37.66            ICD-10 procedure: O2HA0RS, O2HA3RS, O2HA4RS, 5A02116, 5A02216, O2HA0QZ, O2HA3QZ, O2HA4QZ            CPT-4 code: 33975, 33976, 33979, 33981 - 33983, 33977, 33978, 33980
	
13	
History of severe pulmonary disease
	
Measured from all available data to and including day of drug initiation in any diagnosis position and in inpatient or outpatient care setting
 
Worsening Asthma/Status Asthmaticus            ICD-9 diagnosis: 493.01, 493.02, 493.11, 493.12, 493.2x, 493.91, 493.22            ICD-10 diagnosis: J45.21, J45.22, J45.901, J45.902
 
COPD/Chronic Tuberculosis            ICD-9 diagnosis: 491.xx, 492.xx, 494.x, 496, 506.4, 748.61, 011.5x            ICD-10 diagnosis: J41.x, J43.x, J47.x, J44.x, J68.4, Q33.4, A15.0
 
Pulmonary Fibrosis or Interstitial Lung Disease (ILD)            ICD-9 diagnosis: 515, 516.3x, 516.8, 516.9            ICD-10 diagnosis: J84.10, J84.111, J84.112, J84.113, J84.114, J84.115, J84.116, J84.117, J84.09, J84.2, J84.89, J84.9
 
Cystic Fibrosis            ICD-9 diagnosis: 277.0x            ICD-10 diagnosis: E84.xx
 
Pulmonary Hypertension/Other Pulmonary Heart Disease            ICD-9 diagnosis: 416 xx            ICD-10 diagnosis: I27.xx
 
Sarcoidosis
	
Pulmonary fibrosis/Interstitial lung disease:            Jones N, Schneider G, Kachroo S, et al. A systematic review of validated methods for identifying pulmonary fibrosis and interstitial lung disease using administrative and claims data. Pharmacoepidemiol Drug Saf. 2012;21(1):256-60. Available at: http://www.ncbi.nlm.nih.gov/pubmed/22262614.

14	
Diagnosis of peripartum- or chemotherapy-induced cardiomyopathy within the 12 months prior to Visit 1
	
Measured from 365 days prior to and including day of drug initiation in any diagnosis position and inpatient or outpatient care setting
 
Peripartum Cardiomyopathy            ICD-9 diagnosis: 674.5x            ICD-10 diagnosis: O90.3
 
Chemotherapy-Induced Cardiomyopathy            ICD-9 diagnosis: 425.9            ICD-10 diagnosis: I42.7
	
15	
Documented untreated ventricular arrhythmia with syncopal episodes within the 3 months prior to Visit 1
	
Measured 90 days prior to and including day of drug initiation in any diagnosis position and inpatient and outpatient care setting
	
15a	
Documented ventricular arrhythmia within the 3 months prior to Visit 1
	
Measured 90 days prior to and including day of drug initiation in any diagnosis position and inpatient and outpatient care setting
	
	
AND the following:
	
Measured 90 days prior to and including day of drug initiation in any diagnosis position and inpatient and outpatient care setting
	
15b	
Syncopal episodes within the 3 months prior to Visit 1
	
Syncopal Episodes            ICD-9 diagnosis: 780.2            ICD-10 diagnosis: R55
	
	
AND the following:
		

# Appendix A

15c Untreated ventricular arrhythmia within the 3 months prior to visit 1	
Measured 90 days prior to and including day of drug initiation WITHOUT any of these non-drug treatments for ventricular tachycardia in any diagnosis position and inpatient and outpatient care setting
 
Implantable Cardioverter-Defibrillator            ICD-9 diagnosis: V45.00, V45.02, V45.09, V53.32, 996.04, 996.61            ICD-10 diagnosis: Z95.9, Z95.810, Z95.818, Z45.02, T82.110A, T82.111A, T82.120A, T82.121A, T82.190A, T82.191A            ICD-9 procedure: 00.51, 00.54, 37.94 - 37.98            ICD-10 procedure: 02HK0KZ, 02HK3KZ, 02HK4KZ, 02HLOKZ, 02HL3KZ, 02HL4KZ, 0JH609Z, 0JH809Z, 0JH839Z            CPT-4 code: 33220, 33223, 33230, 33231, 33240 - 33249, 33262 - 33264, 33270, 93640 - 93642, 93280 - 93285, 93287, 93289, 93292, 93295
	
OR the following:		
15d Untreated ventricular arrhythmia within the 3 months prior to visit 1	
Measured 90 days prior to and including day of drug initiation WITHOUT any of these oral drug treatments for ventricular arrhythmia in prescription claims
 
Beta-blockers: Acebutolol, Atenolol, Betaxolol, Bisoprolol, Carteolol, Carvedilol, Labetalol, Metoprolol, Metiranolol, Nebivolol, Nadolol, Propranolol, Pindolol, Sotalol, Penbutolol, Oxprenolol
 
Non-DHP CCB: Diltiazem, Verapamil
 
Antiarrhythmic drugs: Amiodarone, Procainamide, Mexiletine, Flecainide, Moricizine
	
16 Symptomatic bradycardia or second- or third-degree atrioventricular block without a pacemaker	
Measured 180 days prior to and including day of drug initiation in any diagnosis position and inpatient and outpatient care setting
 
Second- and Third-degree AV block            ICD-9 diagnosis: 426.0, 426.1x (except 426.11)            ICD-10 diagnosis: I44.2, I44.30, I44.1
	
17 Presence of haemodynamically significant mitral and/or aortic valve disease, except mitral regurgitation secondary to LV dilatation	
Measured 180 days prior to and including day of drug initiation in any diagnosis position and in inpatient and outpatient care setting
 
ICD-9 diagnosis: 394.0, 395.0, 395.2, 396.0, 396.2, V42.2, V43.3            ICD-10 diagnosis: I05.0, I06.0, I06.2, I08.0, Z95.3, Z95.2            ICD-9 procedure: 35.01, 35.02, 35.05, 35.06, 35.11, 35.12, 35.21, 35.22, 35.23, 35.24, 35.97            ICD-10 procedure: 02NF3Z, 02NF4Z, 02NG3Z, 02NG4Z, 02RF372, 02RF38Z, 02RF3JZ, 02RF3KZ, X2RF33Z, 02RF37H, 02RF38H, 02RF3KJ, 027F04Z, 027FDZ, 027FOZ, 02NF0Z, 020F0Z, 027G04Z, 027G0DZ, 027G0Z, 02NG0Z, 02QG0Z, 02VG0Z, 02RF0Z, 02RF08Z, 02RF0KZ, 02RF47Z, 02RF48Z, 02RF4KZ, X2RF03Z, X2RF43Z, 02RF0I, 02RF4I, 02RG0T, 02RG08Z, 02RG0KZ, 02RG37Z, 02RG38Z, 02RG3KZ, 02RG47Z, 02RG48Z, 02RG4KZ, 02RG0I, 02RG3I, 02RG4I, 02UG3I            CPT-4 codes: 33400 - 33403, 33405, 33406, 33420 - 33430, 0257T, 0258T, 0259T
	
18 Presence of other haemodynamically significant obstructive lesions of the LV outflow tract, including aortic and subaortic stenosis	Included in the definition of exclusion criterion # 17	
19 Any surgical or medical condition which might significantly alter the absorption, distribution, metabolism, or excretion of study drugs, including, but not limited to, any of the following:	
Measured 365 days prior to and including day of drug initiation in any diagnosis position in inpatient and outpatient care setting
 
Ulcerative Colitis            ICD-9 diagnosis: 556.xx            ICD-10 diagnosis: K51.xx
 
Crohn's Disease            ICD-9 diagnosis: 555.x            ICD-10 diagnosis: K50.xx
19a History of active inflammatory bowel disease during the 12 months before Visit 1		
OR the following:		
19b Active duodenal or gastric ulcers during the 3 months prior to Visit 1	
Measured 90 days prior to and including day of drug initiation in any diagnosis position in inpatient and outpatient care setting
 
Duodenal Ulcers            ICD-9 diagnosis: 532.0x, 532.1x, 532.2x, 532.3x, 532.9x            ICD-10 diagnosis: K25.0 - K25.3, K25.9
 
Gastric Ulcers            ICD-9 diagnosis: 531.0x, 531.1x, 531.2x, 531.3x, 531.9x            ICD-10 diagnosis: K26.0 - K26.3, K26.9
	
OR the following:		

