Excluded based on Exclusion #15 - Documented untreated ventricular arrhythmia with syncopal episodes	-18	7,353	-6	3,876	-25	8,685
Excluded based on Exclusion #16 - Second- and third-degree AV block	-73	7,280	-29	3,847	-73	8,612
Excluded based on Exclusion #17 - Presence of haemodynamically significant mitral and/or aortic valve disease	-124	7,156	-43	3,804	-246	8,366
Excluded based on Exclusion #19a - History of active inflammatory bowel disease (IBD)	-18	7,138	-12	3,792	-37	8,329
Excluded based on Exclusion #19b - Active duodenal/gastric ulcers	-13	7,125	-8	3,784	-25	8,304
Excluded based on Exclusion #19c - Evidence of hepatic disease	-173	6,952	-80	3,704	-265	8,039
Excluded based on Exclusion #19d - Current treatment with cholestyramine or colestipol resins	0	6,952	0	3,704	-4	8,035
Excluded based on Exclusion #21 - Ivabradine use	-6	6,946	-10	3,694	-4	8,031
Final cohort		6,946		3,694		8,031

\* The Medicare data cut included all patients with a diagnosis for HF, stroke, or diabetes.

† Algorithm provided in Desai et al. (2018).

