# Appendix A

		Measured 365 days prior to drug initiation in any diagnosis position and inpatient care setting	
4b	Hospitalization for heart failure within the last 12 months	
Hospital Admission for CHF
 
ICD-9 diagnosis: 428.x, 398.91, 402.01, 402.11, 402.91, 404.01, 404.11, 404.91, 404.03, 404.13, 404.93
 
ICD-10 diagnosis: I50.1, I50.2x, I50.4, I50.814, I09.81, I11.0, I13.0, I13.2
	
5	Treatment with a stable dose of an ACE inhibitor or an ARB equivalent to enalapril 10 mg/day for at least 4 weeks before the screening visit; and treatment with a stable dose of a beta-blocker for at least 4 weeks prior to the screening visit, unless contraindicated or not tolerated	
Measured 47 days to 2 days prior to drug initiation in prescription claims requiring 28 days supply of oral ACEi or ARB -
 
ACE inhibitors' generic names for prescription claims: Enalapril, Captopril, Clazapril, Fosinopril, Lisinopril, Moexipril, Perindopril, Quinapril, Trandolapril, Zofenopril, Benazepril
 
-OR-
 
ARBs generic names for prescription claims: Candesartan, Eprosartan, Irbesartan, Losartan, Olmesartan, Telmisartan, Valsartan, Azilsartan
	
5a	Treatment with a stable dose of an ACE inhibitor or an ARB equivalent to enalapril 10 mg/day for at least 4 weeks before the screening visit	AND the following:	
5b	Treatment with a stable dose of a beta-blocker for at least 4 weeks prior to the screening visit, unless contraindicated or not tolerated	
Measured 45 days prior to index drug initiation in prescription claims (generic names) of an oral beta-blocker for at least 4 weeks (28 days)
 
Beta-blocker generic names for prescription claims: Acebutolol, Atenolol, Betaxolol, Bisoprolol, Carvedilol, Esmolol, Labetalol, Metoprolol, Metiranolol, Nebivolol, Nadolol, Propranolol, Pindolol, Sotalol, Penbutolol, Oxprenolol
	
6	Although not required, the protocol specified that an aldosterone antagonist should also be considered in all patients, taking account of renal function, serum potassium, and tolerability. If given, the dose of aldosterone antagonist should be stable for at least 4 weeks prior to the screening visit		
EXCLUSION CRITERIA			

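### Exclusions #15 and #16 are written for patients without a treatment or device, but their coding does not exempt patients who have one; the effect on cohort size is about 1% at most

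*Protocol*

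**What the plan says.** **Exclusion #15 (Protocol, Appendix A).** The trial criterion is "Documented untreated ventricular arrhythmia with syncopal episodes within the 3 months prior to Visit 1". It is implemented as 15a (ventricular arrhythmia) and 15b (syncope), plus one of two conditions:

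- 15c looks for patients "WITHOUT any of these non-drug treatments for ventricular tachycardia in any diagnosis position and inpatient and outpatient care setting", followed by ICD codes, over 90 days.
- 15d is "Measured 90 days prior to and including day of drug initiation WITHOUT any of these" oral "drug treatments for ventricular arrhythmia in prescription claims". Its list names 16 beta-blockers, two non-dihydropyridine calcium channel blockers and five antiarrhythmics.

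The connector printed between 15c and 15d is "OR the following".

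**Inclusion #5b (Appendix A).** It is "Measured 45 days prior to index drug initiation in prescription claims (generic names) of an" oral beta-blocker, for at least 28 days. In the Section 5.3 flowchart it comes well before #15.

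**Exclusion #16 (Appendix A).** The trial criterion is "Symptomatic bradycardia or second- or third-degree atrioventricular block without a pacemaker". The implementation gives a 180-day window and AV-block diagnosis codes, with no pacemaker condition. The flowchart label also omits the pacemaker.

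**Exclusion #11 (Appendix A).** It lists pacemaker and ICD codes over 90 days and comes before both #15 and #16 in the flowchart.

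**Counts (Section 5.3; Optum / MarketScan / Medicare).** The row "Excluded based on Exclusion #15 - Documented untreated ventricular arrhythmia with syncopal episodes" removes 18 / 6 / 25. The #16 row removes 73 / 29 / 73.

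**The concern.** A patient is untreated only if both kinds of treatment are absent. Joining the two absence conditions with OR reverses this: lacking either one is enough, and only a patient with both an ICD and a listed drug escapes. In #16 the qualifier that spares paced patients has no counterpart in the code.

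The protocol's aim is to adapt the RCT criteria as closely as the data allow. Neither departure is forced by the data, because Appendix A already holds the drug list and the device codes and already uses a without-treatment construction in 15c and 15d. What is at stake is the fidelity of the eligibility rules and of the flowchart labels. Precision is hardly affected.

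**Working it through.** **1. Flowchart arithmetic reproduces.**
- #15: 7,371 − 18 = 7,353; 3,882 − 6 = 3,876; 8,710 − 25 = 8,685. Total removed: 18 + 6 + 25 = 49.
- #16: 7,353 − 73 = 7,280; 3,876 − 29 = 3,847; 8,685 − 73 = 8,612. Total removed: 73 + 29 + 73 = 175.

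**2. OR against AND, given arrhythmia and syncope.**

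| ICD code | Listed drug | Excluded under OR | Excluded under AND |
|---|---|---|---|
| no | no | yes | yes |
| no | yes | yes | no |
| yes | no | yes | no |
| yes | yes | no | no |

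Only the first row is untreated.

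**3. Which rows can reach #15.** Of the 16 beta-blockers in #5b, 15 are on the 15d list. The exception is esmolol, and #5b asks for an oral drug. The 45-day window of #5b lies inside the 90-day window of 15d. By the written rules, then, anyone who passed #5b has a 15d drug and 15d cannot be true. AND would remove essentially nobody; the flowchart shows 49. That count fits the printed OR, with every removal coming through 15c.

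**4. Interaction with #11.** Most ICD diagnosis codes in 15c also appear in #11, over the same 90 days (V45.00, Z95.9 and Z95.818 are exceptions). As written, 15c is therefore true for nearly everyone who survives #11, and #15 amounts to arrhythmia plus syncope whatever the treatment.

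For #16, a patient with a listed pacemaker code in the last 90 days should already be gone, so the gap covers paced patients whom #11 did not catch. Two things suggest that some remain:
- #11 removed 41/7,969 = 0.5% in Optum and 19/4,173 = 0.5% in MarketScan, against 1,550/11,384 = 13.6% in Medicare.
- After matching, Appendix B still shows the CRT-device covariate at 32.0–33.5% in Optum and MarketScan and 19.2–20.4% in Medicare.

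The covariate's code list is not shown and the Appendix B run has different counts from the flowchart, so this is supportive only.

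**5. Size.**
- Before #17 to #21: 49 + 175 = 224 at most.
- Retention from there on: 18,671 / (7,280 + 3,847 + 8,612) = 18,671 / 19,739 = 94.6%.
- After #17 to #21: 224 × 0.946 ≈ 212, and 212 / 18,671 = 1.1%.

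**6. Power.** Use power = Φ(|ln HR| × √d / 2 − 1.96) with HR 0.8.
- Stated pooled final case: d = 2 × 3,033 × 0.21525 = 1,305.7, which gives 0.9809 and matches the protocol.
- All 224 restored, with matched pairs assumed to grow in proportion: d = 1,305.7 × (1 + 224/18,671) = 1,321.4, which gives 0.982.

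**The case against.** **A background beta-blocker need not count as arrhythmia treatment.** In a cohort that must be on beta-blockers for heart failure, this is a judgement, and AND leaves #15 with almost no effect. Keeping out patients without an ICD could be a deliberate, conservative choice. That stands as a possible intention. It is not what the protocol says: 15d itself lists beta-blockers as treatment, and both criterion and flowchart row say untreated.

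**Exclusion #11 already handles devices.** This stands in part. It narrows the #16 gap, but it looks back 90 days against 180, and its counts in two databases are hard to square with the device prevalence in Appendix B.

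**Three stronger readings are tempting and unsupported.**
- A reader might infer that all 49 patients are known to have been on treatment. This follows from the written definitions only. Matched beta-blocker use in Appendix B is slightly under 100% (for example 1,273 of 1,279 in both Optum arms). That covariate's drug list is not shown, so it neither refutes nor verifies #5b for the 49.
- A reader might infer that all 175 at #16 are paced. The document gives no such count, and 175 is only a ceiling.
- A reader might infer that the cohort is materially less like the RCT population than claimed. The protocol claims only an adaptation as close as possible. Appendix A grades each criterion by a colour that is not legible in the text at hand, so #15 and #16 may already be marked as imperfect.

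**Conclusion.** The coding of #15 and #16 contradicts the criterion text beside it, and no reason is given. For #15, by the written definitions, the 49 removals are of patients on a drug that the protocol itself lists as treatment (esmolol aside). For #16, an unknown share of 175 are paced patients not caught by #11.

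The ceiling is 224 patients before the remaining exclusions, or about 212 (1.1% of 18,671) after them. That assumes the observed 94.6% retention applies to restored patients and that all 175 would return; the true number is probably lower. The same rules apply to both arms, pooled power would move from 0.981 to at most about 0.982, and the effect on the estimate is likely negligible. This is a minor point of fidelity and labelling, and the power and comparison sections do not depend on it.

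**What to change.** - **#15:** replace the OR between 15c and 15d with AND, and state that with #5b in force the criterion then removes almost no one. If patients on drug treatment but without an ICD are meant to be excluded, keep the rule, restate the criterion, relabel the flowchart row and record it as a deliberate departure from the RCT.
- **#16:** add a no-pacemaker-code condition, taking the pacemaker codes from those already under #11 (that list mixes pacemaker and ICD codes) and stating the look-back. If the broader exclusion is intended, say so.
- **#11:** check how it was actually run in each database, since this determines whom the #16 edit can restore. The #16 edit does not bring back patients removed at #11.
- Re-run the flowchart and the tables that depend on it.

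The cost is two edits to Appendix A, one check of executed code and a cohort re-run. No new data are needed.

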# Appendix A

	Variable	Codes and Medications (all medical claims, inpatient and outpatient should be used to define the conditions unless otherwise specified)	Coefficients ("Score")	When Measured for replicating	When Measured ([name]'s algorithm)
1	Intercept	N/A	-1.37219		
2	Cardiomyopathy	ICD-9 diagnosis: 425.x ICD-10 diagnosis: I42.x, I43.x	1.415113	Measured 180 days prior to and including the date of index drug initiation	6 months prior to index date + index date + 30days post-index
3	Diastolic heart failure	ICD-9 diagnosis: 428.3x (not co-occurring with 428.2x ) ICD-10 diagnosis: I50.3x (not co-occurring with I50.2x)	-0.950856	Measured between 180 days prior to and including the date of drug initiation and pick claim closest to the index initiation	on index date
4	Left heart failure	ICD-9 diagnosis: 428.1x (not co-occurring with more specific systolic or diastolic HF codes of 428.2x or 428.3x) ICD-10 diagnosis: I50.1 (not co-occurring with more specific systolic or diastolic HF codes of I50.2x or I50.3x)	0.766415	Measured between 180 days prior to and including the date of drug initiation and pick claim closest to the index initiation	on index date
5	Systolic heart failure	ICD-9 diagnosis: 428.2x (not co-occurring with 428.3x) ICD-10 diagnosis: I50.2x (not co-occurring with I50.3x)	0.754954	Measured between 180 days prior to and including the date of drug initiation and pick claim closest to the index initiation	on index date
6	Myocardial infarction	ICD-9 diagnosis: 410.xx ICD-10 diagnosis: I21.01, I21.02, I21.09, I21.11, I21.19, I21.21, I21.29, I21.3, I21.4, I22.0, I22.1, I22.2, I22.8, I22.9	0.651778	Measured 180 days prior to and including the date of index drug initiation	6 months prior to index date + index date + 30days post-index
7	Unspecified heart failure	ICD-9 diagnosis: 428.0x, 428.4x, 428.9x, 428.2x PLUS 428.3x ICD-10 diagnosis: I50.4x, I50.8x, I50.9, I50.2x PLUS I50.3x	-0.577221	Measured between 180 days prior to and including the date of drug initiation and pick claim closest to the index initiation	on index date

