# Appendix A

22	Beta blocker	Prescription claims for oral: Acebutolol, atenolol, betaxolol, bisoprolol, carteolol, carvedilol, labetalol, metoprolol, nadolol, nebivolol, penbutolol, pindolol, propranolol	0.087257	Measured 180 days prior to and including the date of index drug initiation	6 months prior to index date + index date + 30days post-index
23	Loop diuretic	Prescription claims for oral: Bumetanide, furosemide, torsemide, ethacrynic acid	0.084251	Measured 180 days prior to and including the date of index drug initiation	6 months prior to index date + index date + 30days post-index
24	Rheumatic heart disease	ICD-9 diagnosis: 393 - 398.x ICD-10 diagnosis: I05.xx - I09.xx	-0.073889	Measured 180 days prior to and including the date of index drug initiation	6 months prior to index date + index date + 30days post-index
25	Psychosis	ICD-9 diagnosis: 290.8x, 290.9x, 295.xx, 297.xx, 298.xx, 299.xx, 780.0x - 780.5x ICD-10 diagnosis: Please copy from ICD-10 tab for Psychosis	-0.068198	Measured 180 days prior to and including the date of index drug initiation	6 months prior to index date + index date + 30days post-index
26	Coronary artery bypass graft	ICD-9 procedure: 36.1x, 36.2x ICD-10 procedure: Please copy from ICD-10 tab for CABG CPT code: 33510 – 33536, 33545, 33572	-0.040175	Measured 180 days prior to and including the date of index drug initiation	6 months prior to index date + index date + 30days post-index
27	COPD	ICD-9 diagnosis: 491.xx, 492.xx, 496.xx, 493.2x ICD-10 diagnosis: J41.x, J42.x, J43.x, J44.x	-0.037023	Measured 180 days prior to and including the date of index drug initiation	6 months prior to index date + index date + 30days post-index
28	Sleep apnea	ICD-9 diagnosis: 327.2x, 780.51, 780.53, 780.57 ICD-10 diagnosis: G47.3x	-0.03556	Measured 180 days prior to and including the date of index drug initiation	6 months prior to index date + index date + 30days post-index
29	Hypertensive nephropathy	ICD-9 diagnosis: 403.xx, 404.xx ICD-10 diagnosis: I12.x, I13.xx	-0.03383	Measured 180 days prior to and including the date of index drug initiation	6 months prior to index date + index date + 30days post-index

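### Exclusion 18 (aortic and subaortic stenosis) is declared covered by Exclusion 17, but Exclusion 17's diagnosis codes cover only the rheumatic block and replaced valves, so unoperated non-rheumatic obstruction passes both

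*Protocol*

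**What the plan says.** All of this is in the protocol, Appendix A, unless noted.

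- **Exclusion 17, criterion:** "Presence of haemodynamically significant mitral and/or aortic valve disease, except mitral regurgitation secondary to LV dilatation". The cause of the valve disease is not restricted.
- **Exclusion 17, implementation:** measured over 180 days up to and including drug initiation, any diagnosis position, inpatient and outpatient. The diagnosis lists are "ICD-9 diagnosis: 394.0, 395.0, 395.2, 396.0, 396.2, V42.2, V43.3" and "ICD-10 diagnosis: I05.0, I06.0, I06.2, I08.0, Z95.3, Z95.2". ICD-9, ICD-10 and CPT procedure codes follow, the last being "CPT-4 codes: 33400 - 33403, 33405, 33406, 33420 - 33430, 0257T, 0258T, 0259T".
- **Exclusion 18, criterion:** "Presence of other haemodynamically significant obstructive lesions of the LV outflow tract, including aortic and subaortic stenosis".
- **Exclusion 18, implementation:** "Included in the definition of exclusion criterion # 17". It has no codes, and the flowchart in section 5.3 has no row for it.
- **Ejection-fraction algorithm, row 24**, labelled rheumatic heart disease: "ICD-9 diagnosis: 393 - 398.x ICD-10 diagnosis: I05.xx - I09.xx".
- **Ejection-fraction algorithm, row 2**, labelled cardiomyopathy: "ICD-9 diagnosis: 425.x ICD-10 diagnosis: I42.x, I43.x". These codes are used for prediction and not for Exclusions 17 or 18.

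Sections 1 and 5.2.2 set the aim: follow the trial, and its eligibility criteria, as nearly as the databases permit.

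**The concern.** Exclusion 18 names two conditions and says that another row deals with them. If that row lists no diagnosis for either in its non-rheumatic form, the protocol reports a criterion as implemented when it is only partly so. A patient with a replaced valve is removed, while one whose native valve or outflow tract is obstructed for a non-rheumatic reason, and who has not been operated on, is kept.

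What is at stake is how far the cohort matches the trial population. These are patients the trial meant to keep out, and a reader of the flowchart would believe they had been removed.

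**Working it through.** **1. Diagnosis codes in Exclusion 17 against the protocol's own rheumatic block (row 24)**

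| Listed under Exclusion 17 | Position |
|---|---|
| 394.0, 395.0, 395.2, 396.0, 396.2 | all five within 393 to 398.x |
| I05.0, I06.0, I06.2, I08.0 | all four within I05.xx to I09.xx |
| V42.2, V43.3, Z95.2, Z95.3 | replaced-valve status |

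No other diagnosis code is listed. There is none from 424.x, I34.x or I35.x (non-rheumatic valve disease), and none for congenital subaortic stenosis (746.81, Q24.4) or obstructive hypertrophic cardiomyopathy (425.1x, I42.1). What these absent codes denote is standard ICD content and not text in the protocol. The rheumatic label is the protocol's own.

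**2. Could another step remove these patients?**

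- The procedure codes in Exclusion 17 do so for valve procedures in the 180-day window, whatever the cause.
- Exclusion 9 does so for cardiovascular procedures in its 90-day window.
- 396.0, 396.2 and I08.0 may catch some combined mitral and aortic disease of unspecified cause.
- Exclusion 14 lists only 425.9 and I42.7 among the cardiomyopathy codes.

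What remains is unoperated non-rheumatic aortic stenosis or subaortic obstruction without such a procedure.

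**3. Flowchart (section 5.3), step 17**

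- Optum: 7,280 − 124 = 7,156; 124/7,280 = 1.7%
- MarketScan: 3,847 − 43 = 3,804; 43/3,847 = 1.1%
- Medicare: 8,612 − 246 = 8,366; 246/8,612 = 2.9%
- Pooled: 413/19,739 = 2.1%

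The printed rows reproduce. The counts include patients removed for a replaced valve or a valve procedure, and they do not show how many were missed.

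**4. Number affected (assumed)**

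The prevalence of the missed disease is not given. At 1% to 5% of 3,033 matched patients per arm: 0.01 × 3,033 = 30 and 0.05 × 3,033 = 152.

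**5. Power**

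Power = Φ(√(D/4) × |ln HR| − 1.96), with D the number of events and HR = 0.8. With the plan's pooled D = 1,305.7, √326.4 × 0.2231 − 1.96 = 2.07, so power = 0.981, which is the plan's figure. If correcting the codes cost 1% of these events, power would be 0.980; if 10%, 0.969. Both percentages are assumptions.

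**6. Possible effect on the hazard ratio (illustration)**

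Suppose a fraction p of patients has the missed disease, their baseline risk is k times that of the others, the drug does nothing for them, and the hazard ratio is 0.80 elsewhere. Approximately,

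RR = [(1 − p) × 0.8 + p × k] / [(1 − p) + p × k].

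- p = 1%, k = 1: 0.792 + 0.010 = 0.802
- p = 5%, k = 2: (0.76 + 0.10)/(0.95 + 0.10) = 0.819

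The larger shift is ln(0.819/0.80) = 0.024. The standard error of the log hazard ratio with 1,306 events is about 2/√1,306 = 0.055, so the shift is less than half a standard error.

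**The case against.** Five arguments can be made on the other side.

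- **The procedure codes cover the gap.** They do for patients operated on within the windows. A reader might infer that everyone with non-rheumatic aortic stenosis or outflow obstruction stays in the cohort; the procedure codes show that this is too broad. Unoperated disease still passes.
- **The protocol uses the same block for valve disease in general.** Row 15 of the ejection-fraction algorithm lists 394.x to 397.x, 398.9x, V42.2 and V43.3 under the label valve disorder. A broader label over essentially the same codes adds no non-rheumatic diagnosis, so this does not close the gap.
- **Full ICD-10 lists are held outside the document, and the colours grading how well each criterion maps to claims are not visible in the text.** Both limits are real. However, this cell prints an ICD-10 list, and the appendix says that such lists are converted from ICD-9 codes. The ICD-9 list has the same gap, so there is no reason to expect the conversion to fill it. A flag for poor mapping would also not square with saying that Exclusion 18 is included in 17.
- **Diagnosis codes carry no severity grade, and the criterion asks for haemodynamically significant disease.** This stands as a cost of the remedy. It applies equally to 395.0 and I06.0, which the plan accepts.
- **Comparability is not harmed.** The rule is the same in both arms, and valve disorder is balanced after matching (Appendix B): 254 + 46 + 202 = 502 of 3,033 reference patients (16.6%) against 237 + 49 + 203 = 489 of 3,033 exposed (16.1%). Whether that covariate captures non-rheumatic disease cannot be seen, but no imbalance is shown.

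Two stronger readings are tempting. One is that the missed patients materially pull the hazard ratio towards 1. That rests on an assumed prevalence and an assumed absence of drug effect, and even then the illustrated shift is small. The other is that the ejection-fraction algorithm, which gives cardiomyopathy a weight of 1.415113 and is applied to the reference group, loads the missed patients into one arm. The documents give no count by arm to support this.

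**Conclusion.** The point holds in a limited form. Exclusion 18 is stated to be contained in Exclusion 17, and the listed diagnosis codes do not contain it for non-rheumatic aortic stenosis or for subaortic obstruction in unoperated patients.

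The code comparison needs only the printed lists, the protocol's rheumatic label and the ordinary meaning of the ICD codes. The size is unknown: 30 to 152 patients per arm is an assumed range, not an estimate. Pooled power stays at about 0.97 or above, any movement of the hazard ratio is likely small, and no difference between arms is shown. This is a failure of eligibility fidelity, worth correcting because the study's purpose is to reproduce a trial population and the correction is cheap.

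**What to change.** Before the comparative outcome analysis is run, reconcile the criterion text with the code list:

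- **Exclusion 17:** add non-rheumatic aortic stenosis and non-rheumatic mitral stenosis (for example I35.0, I35.2 and I34.2, with the ICD-9 counterpart for aortic disease, 424.1). Leave out isolated mitral regurgitation, in keeping with the exception in the criterion.
- **Exclusion 18:** give it its own codes for subaortic stenosis (746.81, Q24.4) and obstructive cardiomyopathy (425.11, I42.1), and its own flowchart row.
- **Same scope in both code systems:** 424.1 covers all aortic valve disorders, including regurgitation. If it is used, treat aortic regurgitation the same way in I35.x; otherwise eligibility would depend on which code system was in use.

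Then re-run the flowchart, the propensity-score match and the final power table. If the codes are not added, Appendix A should say that Exclusion 18 is only partly implemented.

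The cost is a code-list edit, a re-run and some loss of patients. Because the codes carry no severity grade, some of those lost will have mild disease, as already happens with the listed codes.
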